8.1.1 Echocardiography protocol

Transthoracic echocardiography (TTE) will be performed in the left lateral decubitus position. Images will be taken from the standard parasternal, apical and subcostal windows. A standard complete exam will be performed and images stored for off-line measurements.³⁶ LV ejection fraction will be calculated from apical 4 and 2 chamber views using Simpson’s biplane rule. A cut-off of less than or equal to 40% will be used for inclusion in the trial. Contrast agents will not be used.

After screening echocardiography, suitable patients will be approached for consent to take part in the trial as described above. Patients who have consented will undergo the following tests at least 3 months post myocardial infarction and prior to randomisation to either sacubitril/valsartan or valsartan.

8.2 Pre-randomisation investigations

The following investigations will be performed prior to randomisation and all results recorded in the eCRF.

- Full physical examination – including measurement of height, weight and resting heart rate and blood pressure
- A record of the patients past medical history will be obtained. The presence of diabetes mellitus (Type-1 or Type-2), hypertension, hyperlipidaemia, cerebrovascular disease, peripheral vascular disease, chronic obstructive pulmonary disease and smoking history will be recorded. Prescribed medication pre-randomisation will also be recorded.
- 12-lead ECG
- Spot urine collection
- Venepuncture – 50ml of venous blood withdrawn for biochemical, biomarker and hormonal analysis and baseline renal/liver function for trial eligibility
- Cardiac MRI with gadolinium contrast

8.2.1 Biochemical and hormonal measurements

50mls of venous blood will be collected at three time points during the study - pre-randomisation, study visit 7 (26 weeks) and study visit 9 (52 weeks) for biochemical and hormonal analysis. Where possible, samples will be taken as fasting, early morning samples to account for the diurnal variation in hormonal measurements. Non-fasting samples will be taken in patients with diabetes to avoid any potential risk of hypoglycaemia. All samples will be taken after at least 15 minutes of supine rest. Spot urine collections will be performed at pre-randomisation, 26 weeks and 52 weeks. Samples will be used for the following measurements pertaining to the action of sacubitril/valsartan and remodelling: Brain Natriuretic Peptide (BNP), N-Terminal pro BNP (NT-proBNP), MR-pro Atrial Natriuretic Peptide (MR-proANP), C-terminal ANP, C-type natriuretic peptide (CNP), high sensitivity Troponin-I (hsTnI), Urea and Electrolytes (U&Es), C-Reactive Protein (CRP), cyclic guanosine monophosphate (cGMP), neprilysin antigen, matrix metalloproteinases (MMPs), Tissue inhibitors of metalloproteinases-1 (TIMP-1), ST2, galectin-3, amino-terminal propeptide of type III procollagen (PIIINP), adrenomedullin (MR-proADM), growth differentiation factor (GDF-15), and endothelin-1. Measurements of glycated haemoglobin A1c (HbA1c) will be made as per standard clinical practice at baseline, 6 months and 12 months for the purposes of screening for, and assessment of diabetic control. Any samples remaining will be stored for analysis of any future relevant biomarkers as they become available and for use in future ethically approved research studies if appropriate.

8.2.2 CMR protocol

All CMR scans will be performed on a single 3.0 Tesla Siemens MAGNETOM Prisma scanner located in the CRF at the QEUH. The MRI scan will include cine MRI, T1 and T2 maps, strain encoded MRI, and contrast enhanced imaging including first pass perfusion at rest, microvascular obstruction and late gadolinium enhancement imaging 10 - 15 min after contrast administration. IV access will be required for contrast administration and a full blood count will be obtained before the scan in order to measure extracellular volume. Specific details of the CMR protocol are detailed in a local Standard Operating Procedure. Patients will be provided with an MRI information sheet prior to their visit (Appendix 2).

8.3 26-week visit

This will comprise of a half-day visit to the QEUH CRF. A number of the baseline investigations will be repeated:

- full physical examination
- spot urine collection
- venepuncture – 50ml blood withdrawn for biochemical and hormonal analysis

Patients will also be asked to complete a short patient global assessment questionnaire (Appendix 3) at this visit.

8.4 52-week visit (+/- 3 months)

This will comprise of a half-day visit to the QEUH CRF. A number of the baseline investigations will be repeated:

- full physical examination
- spot urine collection
- venepuncture – 50ml blood withdrawn for biochemical and hormonal analysis
- cardiac MRI with gadolinium contrast will be performed.

Patients will also be asked to complete a short patient global assessment (Appendix 3) questionnaire at this visit.

In response to the COVID-19 pandemic we have allowed an extension of the patients IMP treatment by up to 3 months. During this extended time on IMP we would anticipate following up with patients by telephone every 6 weeks. Patients have the clinical research team contact details should they wish to discuss any aspect of the extended involvement themselves.

At this point a patient's participation in the involvement in the trial will end. They will return any unused study drug. Following their involvement in the trial patients will be converted to an ACE-inhibitor or ARB as per local practice guidelines at an equivalent dose to their final study drug dose level. Prior to commencement of any ACE-inhibitor, patients will require to have a 36-hour washout period following their last dose of study drug in order to reduce the risk of angioedema associated with combined ACE and NEP inhibition.

8.5 Definition of end of trial

The end of the trial is defined as the date of the last patient's 52-week (+/- 3 months) study visit plus additional 30 days of event reporting.

9 Assessment, samples and data collection

Trial data will be recorded on trial-specific eCRFs. Only the patient's unique identifier number, date of birth and initials will be recorded on the eCRF in order to identify the patient. Any missing or discrepant data queries will be sent to appropriate research

team member(s) to be reviewed. Biochemical samples will be stored in the QUEH Biochemistry department and the BHF Glasgow Cardiovascular Research Centre to be analysed in batches on completion of the trial. Analysis of echocardiograms and CMR imaging will be performed offline.

Table 9-1 Schedule of Assessments

Study Procedure	Screening (>3months post myocardial infarction)	Visit 1 - Randomisation (Week 0)	Visit 2 (Week 1 ± 3 days)	Visit 3 (Week 2± 3 days)	Visit 4 (Week 4± 3 days)	Visit 5 (Week 5± 3 days)	Visit 6 (Week 14 ± 7 days)	Visit 7 (Week 26 ± 7 days)	Visit 8 (Week 39 ± 7 days)	Visit 9 (Week 52 ± 3 months)
Review Inclusion/Exclusion Criteria	X									
Echocardiogram	X									
Obtain informed consent	X	X								
Cardiac MRI		X								X
Physical examination		X	X		X			X		X
Medical history	X	X								
Concomitant medications	X	X	X	X	X	X	X	X	X	X
Vital Signs (Blood pressure/Heart rate)	X	X	X	X	X	X	X	X	X	X
12 Lead ECG		X								
Spot urine collection		X						X		X
Venepuncture (Urea and Electrolytes/FBC and LFTs)	X&	X	X	X	X	X	X	X	X	X
Venepuncture (Biochemical/hormonal/biomarker analysis)		X						X		X
Pregnancy testing in WoCBP		X			X		X	X	X	X
Patient global assessment questionnaire								X		X
IMP Dispensing*		X			X		X	X		
Up-titrate IMP#					X					
IMP Administration+		X	X	X	X	X	X	X	X	X
Adverse event reporting			X	X	X	X	X	X	X	X
Study completion										X

* Study drug will be introduced at equivalent dose to existing ACE-i/ARB treatment (Dose level 2 or 3) at investigator's discretion

#Up-titration not required if patient already on dose level 3 but down titration to dose level 2 permitted in response to COVID-19

&If not done in the preceding 6 months

+Emergency IMP dispensing permitted during COVID-19 pandemic

10 Pharmacovigilance

10.1 Definitions

Table 10-1 Pharmacovigilance Definitions

Term	Definition
Adverse Event (AE)	Any untoward medical occurrence in a participant to whom a medicinal product has been administered, including occurrences which are not necessarily caused by or related to that product.
Adverse Reaction (AR)	An untoward and unintended response in a participant to an investigational medicinal product which is related to any dose administered to that participant. The phrase "response to an investigational medicinal product" means that a causal relationship between a trial medication and an AE is at least a reasonable possibility, i.e. the relationship cannot be ruled out. All cases judged by either the reporting medically qualified professional or the Sponsor as having a reasonable suspected causal relationship to the trial medication qualify as adverse reactions.
Serious Adverse Event (SAE)	A serious adverse event is any untoward medical occurrence that: results in death is life-threatening requires inpatient hospitalisation or prolongation of existing hospitalisation results in persistent or significant disability/incapacity consists of a congenital anomaly or birth defect Other events that are considered medically significant may also be considered serious if they jeopardise the participant or require an intervention to prevent one of the above consequences. NOTE: The term "life-threatening" in the definition of "serious" refers to an event in which the participant was at risk of death at the time of the event; it does not refer to an event which hypothetically might have caused death if it were more severe.
Serious Adverse Reaction (SAR)	An adverse event that is both serious and, in the opinion of the reporting Investigator, believed with reasonable probability to be due to one of the trial treatments, based on the information provided.
Suspected Unexpected Serious Adverse Reaction (SUSAR)	A serious adverse reaction, the nature and severity of which is not consistent with the information about the medicinal product in question set out:

	
in the case of a product with a marketing authorisation, in the summary of product characteristics (SmPC) for that product.
 
in the case of any other investigational medicinal product, in the investigator's brochure (IB) relating to the trial in question.

--	--

10.2 Recording and reporting of Adverse Events

All AEs occurring during the trial that are observed by the Investigator or reported by the participant should be recorded in the participant's medical records whether or not attributed to trial medication.

Details of the following adverse reactions will be collected within the eCRF at all follow up visits from randomisation until the participants' final visit.

- Clinically relevant hypotension (syncope, dizziness, etc)
- Worsening renal function
- Acute kidney injury
- Hyperkalaemia
- Occurrence of angioedema

The seriousness of each adverse reaction will be collected along with the outcome of the event at the time of the visit i.e. whether the reaction is ongoing at the time of the visit or the participant has recovered.

SAEs will be documented within the eCRF and will be collected from the date of randomisation until 30 days post cessation of trial treatment to allow for reporting of any ongoing adverse reactions associated with the use of the trial drug.

The following events are excluded from the need for expedited reporting:

- Routine treatment or monitoring of the studied indication not associated with any deterioration in condition.
- Treatment which was elective or pre-planned, for a pre-existing condition not associated with any deterioration in condition, e.g. pre-planned hip replacement operation which does not lead to further complications.
- Any admission to hospital or other institution for general care where there was no deterioration in condition.
- Treatment on an emergency, outpatient basis for an event not fulfilling any of the definitions of serious as given above and not resulting in hospital admission.

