2.5.2. ADVERSE EVENTS OF INTEREST

Adverse events of interest include:

- Worsening renal function or acute kidney injury
- Hyperkalaemia
- Symptomatic hypotension
- Symptomatic hypotension with systolic BP <90mmHg
- Angioedema
- Cough

The number and percentage of subjects experiencing one of the adverse events of interest listed will be summarised overall and by randomised treatment group. The Fisher's Exact test will be used to assess whether there is a statistical difference between number of subjects experiencing each event between treatment groups. The following event details will also be summarised and compared between groups: seriousness criteria, severity, relationship to study drug and details of action taken. Full details of these events are provided in section 10.2 of the study protocol.

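### Protocol 10.2 as worded takes the listed non-serious events into the eCRF only if judged possibly drug-related, while SAP 2.5.2 compares adverse events of interest between arms

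*Protocol*

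**What the plan says.** Protocol Table 10-1 separates two terms. An adverse event is any untoward occurrence, "including occurrences which are not necessarily caused by or related to that product". An adverse reaction needs more: that "a causal relationship between a trial medication and an AE is at least a reasonable possibility, i.e. the relationship cannot be ruled out".

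Protocol 10.2 uses both terms close together. Adverse events of every kind "should be recorded in the participant's medical records whether or not attributed to trial medication". For the database the rule is different: "Details of the following adverse reactions will be collected within the eCRF", at each follow-up visit up to the last. Five types follow: clinically relevant hypotension, worsening renal function, acute kidney injury, hyperkalaemia and angioedema. The details named for them are seriousness and outcome.

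Serious events have their own route, with no causality condition: "SAEs will be documented within the eCRF and will be collected from the date of randomisation until 30 days post cessation of trial treatment". Protocol 10.4 confirms that all of them are reported through the eCRF.

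SAP 2.5.2 speaks of events, not reactions: "The number and percentage of subjects experiencing one of the adverse events of interest listed will be summarised", overall and by arm, with Fisher's exact test. It also summarises severity, relationship to study drug and action taken, and refers the reader to protocol 10.2 for details of the events.

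**The concern.** A site that applies the protocol's own definitions would not enter a non-serious hyperkalaemia or renal decline that it put down to another cause. The SAP table would then be read as a count of events when it is a count of events attributed to the drug. Rates would be understated, and the reader could not tell by how much.

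The protocol also makes other explanations likely to turn up. After a fall in renal function, section 6.8.1 has investigators look for NSAIDs, antibiotics, hypovolaemia and urinary infection. After a raised potassium, section 6.8.2 has them review supplements, potassium-sparing diuretics, trimethoprim and salt substitutes. These are events on the 10.2 list.

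SAP 2.5.2 is the only planned comparison of non-serious clinical events between arms. A filter at data entry would therefore not be made good elsewhere in the analysis.

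**Working it through.** The documents give no expected event rates and no attribution share. The main check is therefore a comparison of texts, followed by an illustration on assumed figures.

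**1. What can reach the database, by type of event**

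| Event | Route in the protocol | Planned analysis |
|---|---|---|
| Serious, any cause | eCRF (10.2, 10.4) | SAP 2.5.3; related events are a subset |
| Non-serious, listed, judged possibly related | eCRF (10.2) | SAP 2.5.2 |
| Non-serious, listed, judged unrelated | Medical records only (10.2 read with Table 10-1) | None |
| Non-serious cough | Medical records only (not on the 10.2 list) | SAP 2.5.2 lists it |

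The third row is the gap. The fourth is a related mismatch: the SAP adds cough, and refers to a protocol section that does not list it.

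**2. Would the filter leave a trace?** Protocol 10.3 requires a causality assessment for serious events only, and 10.2 names only seriousness and outcome for the listed reactions. The protocol therefore does not require a causality record for non-serious events. Nothing in the database would show what had been left out.

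**3. Does another planned analysis compensate?** Table 9-1 schedules blood pressure and urea and electrolytes at every follow-up visit. The SAP's safety section covers withdrawal, events of interest and serious events, with no follow-up laboratory or blood-pressure summary. Derivation is feasible but not planned.

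**4. Illustration (assumed figures).** Let *p* be the true proportion of patients with a listed non-serious event and *q* the share judged possibly related. With at most one such event per patient, the observed proportion is *p* × *q*.

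- *p* = 20%, *q* = 1: 20%
- *p* = 20%, *q* = 0.75: 15%
- *p* = 20%, *q* = 0.5: 10%

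The same share in both arms also weakens the comparison. Exact power of a two-sided Fisher test at 0.05, with 50 patients per arm (100 randomised 1:1) and observed rates *p* × *q*:

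| Assumed true rates | *q* = 1 | *q* = 0.75 | *q* = 0.5 |
|---|---|---|---|
| 10% v 20% | 20% | 12% | 6% |
| 10% v 30% | 64% | 45% | 24% |
| 15% v 40% | 76% | 57% | 33% |

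**5. If the share differed by arm (also assumed).** With a true rate of 20% in both arms and *q* of 0.7 and 0.5, the observed rates are 20% × 0.7 = 14% and 20% × 0.5 = 10%, that is 7/50 v 5/50. Fisher's exact p is 0.76, so this example would not produce a false signal.

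**The case against.** The strongest reply is that 10.2 is loosely worded and describes no gate. The section is headed as covering adverse events, Table 9-1 schedules adverse event reporting at Visits 2 to 9, and no passage makes a causality judgement a condition of eCRF entry. The SAP's plan to summarise relationship to study drug suggests that the form has a causality field and may hold unrelated events. The eCRF is not in the documents. This stands in part: actual loss cannot be shown. It does not settle the matter, because the one sentence that states the collection rule uses the narrower of two terms that the protocol itself defines.

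Second, the definition of a reaction is broad: a relationship need only be impossible to rule out. The protocol describes both drugs as potentially nephrotoxic and able to cause hypotension, and treats hyperkalaemia as a risk on study drug. Many listed events would qualify, so a share of 0.5 may be pessimistic. That stands, and is why a range is shown.

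Three stronger readings are tempting, and the documents do not support them:

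- **That only reactions enter the eCRF.** All serious events do, whatever their cause.
- **That the comparison is biased between arms.** The trial is double-blind and double-dummy, both arms contain valsartan, and nothing in the documents indicates that attribution differs by arm.
- **That the relationship table would be worthless.** Protocol 10.3 grades a related event as possible, probable or definite, so a table of related events could still carry information. It could not show how many non-serious events were judged unrelated.

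Finally, protocol 11.3 plans safety summaries without formal comparison, and the primary endpoint is untouched. Both are true, but the counts themselves are affected whether or not they are tested.

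**Conclusion.** The point holds in a limited form. Protocol 10.2, read with Table 10-1, restricts eCRF capture of the five listed non-serious event types to those judged possibly drug-related, and SAP 2.5.2 analyses them as adverse events. Only non-serious events judged unrelated can be lost. This is a risk that follows from the wording, not a demonstrated loss.

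Its size is unknown, and the figures above rest wholly on assumed event rates and attribution shares. The conclusion also assumes that sites apply the protocol's definitions as written and that the eCRF follows them. If the form in fact takes events regardless of cause, the protocol misdescribes the data and the wording still needs correcting. The change is worth making because it removes an attribution filter from the only planned between-arm comparison of non-serious clinical events, at little cost.

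**What to change.** **Protocol 10.2.** For the listed events, replace the term adverse reactions with adverse events, whether or not considered related. Name causality as a separate eCRF field.

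**SAP 2.5.2.** Align it with that rule, so that the event list and the details summarised (severity, relationship, action taken) match what protocol 10.2 says is collected, including the SAP's added items: cough, and symptomatic hypotension with systolic pressure below 90 mmHg.

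**If data collection is already complete under the narrower rule.** Add to SAP 2.5.2 a by-arm summary of hyperkalaemia and renal decline derived from the scheduled urea and electrolyte values. Fix the analysis thresholds before unblinding: the protocol gives several potassium and renal cut-offs for management and alerts, but labels none as the event definition. Label the eCRF list as attributed reactions in the tables. Laboratory derivation does not recover angioedema or symptomatic hypotension, so those two would remain attributed counts.

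**Cost.** One wording change and slightly more eCRF entry, plus a form change if no causality field exists; or, after collection, threshold definitions and a small amount of programming.

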10.3 Assessment of adverse events

All adverse events must be assessed for seriousness. SAEs occurring between the date of consent and 30 days post treatment must be assessed for causality,

expectedness and severity and notified to the Sponsor. This is the responsibility of the CI or designee.

Seriousness

AEs should be assessed for seriousness as per the definitions in section 10.1; those meeting the criteria for an SAE are subject to expedited reporting to the sponsor.

Assessment of causality

SAEs must be assessed for their causality i.e. does the event have a reasonable causal relationship with the trial medication.

Assessment of expectedness

If an SAE is considered to be related (possibly, probably or definitely) to the study medication, an assessment should be made of the expectedness of the reaction i.e. is the reaction a recognised adverse effect of the medication.

The expectedness of an adverse reaction must be assessed against the Reference Safety Information (RSI) i.e. the list of expected reactions detailed in the Summary of Product Characteristics (SmPC) for the Investigational Medicinal Product approved during Clinical Trial Authorisation process.

Expected: consistent with the relevant product information documented in the RSI.

Unexpected: not consistent with the relevant product information documented in the RSI.

Assessment of Severity

This should be assessed and described using the following categories:

- Mild-awareness of event but easily tolerated
- Moderate-discomfort enough to cause some interference with usual activity
- Severe-inability to carry out usual activity.

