10.4 Reporting to sponsor (Pharmacovigilance Office)

All SAEs arising during the study will be reported by the Principal Investigator (or designee) to the sponsor (PV Office) by completing the trial eCRF as soon as reasonably practicable and in any event within 24 hours of first becoming aware of the event. Any follow up information should also be reported.

In the event that eCRF reporting is not possible, a paper SAE form (CTIMP) can be downloaded from the Glasgow Clinical Trials Unit website: www.glasgowctu.org.

This should be completed and faxed to the PV Office. ([contact]). A copy of the complete form should be placed in the Study Site File. If necessary, a verbal report can be given by contacting the PV Office on [name]

[name]/ [name]. This must be followed up as soon as possible with a written report.

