2.5.3. SERIOUS ADVERSE EVENTS

The number of serious adverse events will be reported and the following event details will be summarised for the randomised population overall and by treatment group: seriousness criteria, severity, relationship to the study drug, expectedness, event outcome and SAE duration (if recovered or fatal).

The number and percentage of subjects experiencing at least one serious adverse event will be reported and summarised by Medical Dictionary for Regulatory Activities (MedDRA) System Organ Class (SOC) and Preferred Term (PT). The Fisher's Exact test will be used to assess whether there is a statistical difference between the number of subjects with each type of event between treatment groups.

The same summaries will be provided for the subsets of serious adverse events that are (a) at least possibly related to the study treatment, (b) Suspected Unexpected Serious Adverse Reactions (SUSARs) and (c) fatal, (d) prior to 1st March 2020 and (e) experienced on or after 1st March 2020.

All serious adverse events will be listed.

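### Protocol 10.2 and 10.3 close the SAE window 30 days after study drug stops, 10.4 and 8.5 tie it to the study, and the SAP's by-arm SAE comparison states no window

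*Protocol*

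**What the plan says.** Four protocol sections bear on when SAE collection ends.

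- Section 10.2 documents SAEs in the eCRF from randomisation "until 30 days post cessation of trial treatment to allow for reporting of any ongoing adverse reactions".
- Section 10.3 has the same end: "SAEs occurring between the date of consent and 30 days post treatment must be assessed for causality", together with expectedness, severity and notification to the sponsor. Its start differs from 10.2 (consent, not randomisation), but that is not the issue here.
- Section 10.4 has no treatment-based limit: "All SAEs arising during the study will be reported by the Principal Investigator (or designee) to the sponsor".
- Section 8.5 defines the end of the trial by the last patient's "52-week (+/- 3 months) study visit plus additional 30 days of event reporting".

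Section 10.2 also names five adverse reactions (clinically relevant hypotension, worsening renal function, acute kidney injury, hyperkalaemia, angioedema). These are collected, with their seriousness, "at all follow up visits from randomisation until the participants' final visit", whether or not the patient is still on drug.

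On the analysis side, protocol 11.3 specifies intention to treat and SAP 2.1 takes all randomised subjects. For SAEs, SAP 2.5.3 says that "the following event details will be summarised for the randomised population overall and by treatment group". It repeats the summaries for related, SUSAR and fatal subsets, and compares the number of subjects with each type of event by Fisher's exact test. It gives no observation period.

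Protocol 6.5 and SAP 2.2 both name withdrawal from study medication and withdrawal from follow-up as separate events. Neither document says how long a patient who stops drug is then followed.

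**The concern.** A by-arm comparison of the proportion of patients with an SAE is fair only if both arms are watched for the same time. Under 10.2 and 10.3 the length of observation depends on how long the patient stays on drug, which is itself a consequence of tolerability and clinical course. Renal decline, hyperkalaemia and new heart failure are all routes off study drug in 6.5 and 6.8, and patients who take them may well have a higher risk of a later hospitalisation or death. If one arm is stopped more often, its SAE count is taken over a shorter time and looks better than it should.

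Two practical effects follow. An investigator cannot tell from the protocol whether a hospitalisation at week 20, after a permanent stop at week 8, has to be entered. And a late death could appear as such in the attendance table of SAP 2.2 while being absent from the fatal subset in SAP 2.5.3.

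**Working it through.** **1. The rules side by side.** Take a patient whose last dose is at time s and whose final visit is at time F.

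| Source | End of collection or reporting |
|---|---|
| Protocol 10.2, SAEs in the eCRF | s + 30 days |
| Protocol 10.3, assessment and notification | s + 30 days |
| Protocol 10.4, reporting to sponsor | no limit other than the study |
| Protocol 8.5, end of trial | last patient's 52-week visit + 30 days (a trial-level date) |
| Protocol 10.2, five listed reactions | F |
| SAP 2.5.3 | not stated |

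For a patient who takes drug up to the final visit, s = F and the rules agree in substance. They diverge only when s + 30 days falls before F, that is, after an early permanent stop in a patient who is still followed.

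**2. The plan's own figure.** The documents give no SAE rate and no rate of stopping study drug. Their only design calculation is in protocol 11.1: difference 6 mL/m², SD 7.8 mL/m², 45 per arm, alpha 0.05 (taken as two-sided).

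- Power = Φ(6 / (7.8 × √(2/45)) − 1.96) = Φ(3.65 − 1.96) = 95.4%, consistent with the stated figure of more than 90%.
- 90 / (1 − 0.10) = 100 patients, as stated.

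This reproduces and is unaffected by the present point. The 10% in it covers loss to follow-up, heart failure or death, so it is not a rate of stopping drug.

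**3. One patient who stops permanently and stays in follow-up.** Planned follow-up is taken as 52 weeks. A final visit later in the ± 3-month window lengthens the gap and an earlier one shortens it.

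Uncollected share = (52 − (stop week + 30/7)) / 52

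| Stop week | Window closes (week) | Weeks uncollected | Share of 52 weeks |
|---|---|---|---|
| 8 | 12.3 | 39.7 | 76% |
| 13 | 17.3 | 34.7 | 67% |
| 26 | 30.3 | 21.7 | 42% |

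From day 334 (364 − 30) onwards a stop leaves no gap.

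**4. The whole trial.** Assumptions: a proportion d of patients stops permanently, stop times are uniform over 364 days, and all of them stay in follow-up.

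- Mean uncollected days per stopper = 334² / (2 × 364) = 153.2.
- As a share of 364 days: 153.2 / 364 = 42.1%.
- Share of all planned follow-up = d × 42.1%.

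| Assumed d | Follow-up uncovered |
|---|---|
| 5% | 2.1% |
| 10% | 4.2% (10 × 153.2 / 365.25 ≈ 4.2 patient-years in 100 patients) |
| 20% | 8.4% |
| 30% | 12.6% |

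**5. Difference between arms.** On the same assumptions, every 10 percentage points of difference in stopping between arms opens a gap of 0.10 × 42.1% = 4.2 percentage points in the follow-up over which SAEs are collected.

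**The case against.** The strongest reply is that 10.4, read literally, already captures the late events. Every SAE during the study is to be reported through the eCRF within 24 hours, 10.6 makes the investigator responsible for recording and reporting all of them, and Table 9-1 has adverse event reporting at each visit up to Visit 9. A reader might infer from 10.2 that such events are excluded by rule. The documents do not support that: they contain two incompatible rules, and which one sites follow is unknown. This part of the reply stands.

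A reader might also infer that everyone who stops drug is followed to week 52. No passage says so. Section 6.5 asks those starting open-label sacubitril/valsartan, or withdrawing, at 6 months or later for an end-of-study CMR, and asks for none before 6 months. Angioedema cases (6.8.4) and pregnancies (5.3) leave the study altogether. Separate withdrawal categories and intention to treat make continued follow-up possible; they do not schedule it. Nor is every stop a cessation: 6.5 and 6.8 provide for temporary interruption and re-challenge.

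Finally, some late events are kept in any case: the five listed reactions run to the final visit, and SAP 2.2 classifies non-attenders who have died.

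Three things survive.

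- Reinfarction, heart-failure admission and death are not on the list of five reactions.
- Even where 10.4 brings a late SAE in, 10.3 does not call for causality or expectedness to be assessed after 30 days, so the related and SUSAR subsets in SAP 2.5.3 could be incomplete.
- Protocol 11.3 plans safety summaries without formal comparison, whereas the SAP tests. But unequal observation distorts a descriptive table as much as a test.

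**Conclusion.** The concern holds as an internal contradiction with an unstated analysis window. Sections 10.2 and 10.3 cannot both be followed together with 10.4 for a patient who stops drug early and remains in follow-up, and SAP 2.5.3 does not say which period its comparison covers. If sites work to 10.2 and 10.3, SAEs other than the listed reactions can be missed from 30 days after a permanent stop, unevenly if stopping differs by arm.

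For the individual patient the gap is large: 76%, 67% or 42% of 52 weeks for a stop at week 8, 13 or 26. For the trial it is modest: about 2% to 13% of planned follow-up for 5% to 30% stopping. The trial-level range rests on an assumed stopping rate, uniform stop times and continued follow-up of every stopper. Fewer patients staying in follow-up, or more temporary stops, would make it smaller; earlier stops would make it larger.

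A reader might go further and infer that the safety conclusion is biased, or that enough events are lost to alter a Fisher result. That would need permanent stopping that differs by arm, continued follow-up of those patients, and sites applying 10.2 over 10.4. The documents establish none of these and give no SAE rate from which to count lost events.

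**What to change.** In protocol 10.2 and 10.3, align the end of the SAE window with 10.4 and 8.5: collect and assess SAEs to the later of the patient's final study visit and 30 days after the last dose, for every randomised patient still in follow-up, including those off study drug or on open-label treatment. State in the protocol how long patients who stop drug are followed, so that the final visit is defined for them.

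In SAP 2.5.3, name this common window as the basis of the by-arm SAE tables and tests, and give the count up to 30 days after last dose as a secondary on-treatment table.

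The cost is a short amendment to the wording, a few more SAE forms and one extra table. Sample size and power do not change, and patients already attending need no new visits. The change does not reach patients who are withdrawn from the study, such as angioedema cases; their shorter observation should be visible in the disposition table.
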